12.1.1 Stratified Presentation

Primary BoExp summaries will be produced by arm, sex (male vs. female), CC consumption (10-19 CC/day vs. >19 CC/day) and time point (if applicable), unless otherwise stated.

12.1.2 Subgroup Analyses

No subgroup analyses will be performed in this study.

12.1.3 Descriptive Statistics

For continuous data, summary statistics will include the number of subjects (n), the number and percent of subjects with missing data, the arithmetic mean, arithmetic SD, median, first and third quartiles, minimum, maximum, and number; for log-normal data the geometric mean and geometric CV will also be presented. For categorical data, frequency counts and percentages will be presented. Data listings will include all subject level data collected unless otherwise specified. Summary statistics and statistical analyses will generally only be performed for subjects included in the relevant analysis population. For the calculation of summary statistics and statistical analysis, unrounded data will be used.

Summaries on the Safety Population will be produced by actual exposure, including the additional set of subjects who tested the product but were not enrolled or were discontinued from enrollment before randomization.

The following product labels will be used throughout the TFLs (Table 17):

Table 17: Product Labels

Product	Format used in TFLs	Order in TFLs
Tobacco Heating System 2.2	THS 2.2	1
Conventional cigarettes	CC	2
Smoking abstinence	SA	3

The following stratification labels (Table 18) for the TFLs will be used:

Table 18: Stratification Labels

Stratification Factor	Definition
Sex	male female
Daily CC consumption (per day)	<10 ¹ 10-19 >19

¹ Note that due to inclusion criteria for the study there should not be any subjects with CC consumption <10, therefore this category will not be presented unless there is sufficient data for analysis/presentation (see Section 12.1.5.1 "Insufficient Data for Analysis/Presentation").

12.1.4 Definitions for Statistical Data Analysis

The following definitions (Table 19) for statistical analyses/presentations will be used:

Table 19: Definition of terms for the statistical analysis

Term	Definition
Baseline Value	The last assessment prior to 06:29 AM on Day 1

N.B. For data where baseline is different to the above will be defined in the specific section of the SAP.

For urine collections taken on Days x to y, e.g., Days 5 to 6, these will be referred to as collected on Day x, i.e., Day 5, in the SAP.

12.1.5 Handling of Dropouts or Missing Data (including outside the limits of quantification)

In general, missing data will not be imputed in this study, due to the nature of the measurements and the short periods of exposure and use. However, for questionnaire data

total scores and domain or subscale scores may use a certain degree of imputation (by averaging across individual item scores) as detailed in Section 7.3 “Questionnaires”.

Laboratory parameters will be presented as detailed in Section 7.1 “Biomarkers”.

12.1.5.1 Insufficient Data for Analysis/Presentation

If there are no values/events at the general value then the break out should not be presented. For example if the number of related AEs is zero then no presentation by severity of related events at the single level will be produced.

Some of the TFLs will not have sufficient numbers of subjects or data for presentation. If this occurs, the blank TFL shell will be presented with a message printed in the center of the table, such as, “No serious adverse events occurred for this study.”

For categories of summaries that have <4 subjects no summaries will be shown.

12.1.6 Handling of Unplanned Data

Unscheduled post-product use readings will be excluded from the summary statistics. Unscheduled readings will be labelled as unscheduled in the listings and mapped to the study day using the date of the study day until midnight.

12.1.7 Multiple Comparisons / Multiplicity

The primary endpoints will be tested using a multiple testing procedure to preserve the overall alpha level by simultaneously testing the endpoints using a closed procedure with each test performed at an alpha level of 5%. This implies that statistical significance is required for all primary endpoints in order to be able to make confirmatory claims about any of the endpoints.

No adjustment will be made on any of the secondary endpoints.

12.2 Disposition of Subjects

The number and percent of subjects will be summarized for the following categories: subjects screened, screening failures that tried product, screening failures that did not try product, enrolled subjects, enrolled and not randomized, randomized subjects, completed, and discontinued (if applicable discontinued subject that never used their allocated products will be identified).

Subjects in the Safety Population will be displayed by actual exposure.

Inclusion and exclusion criteria will be listed as to whether the subjects have met or not met the criteria.

All subjects who fail to complete the study will be categorized by their primary reason for discontinuation and summarized by actual exposure. Disposition of subjects and reasons for withdrawal will also be summarized separately. Supportive listings will be provided.

The number and percent of randomized subjects with protocol deviations and the number of protocol deviations will be summarized by actual exposure, broken down by main deviation category (major/minor) and sub-categories. Subjects will be counted once per deviation category, and can be counted for more than one deviation category.

Supportive listing will be provided, including any additional comments for tests that are not performed to be included on the listings of individual data.

The data will be presented in the below outputs, the TFL number refers to the TFL number in the accompanying TFL shell document:

TFL number	Title
TABLES	
15.2.1.1	Summary of Subject Disposition – All Screened Subjects
15.2.1.2	Summary of Reasons for Discontinuations – All Randomized Subjects
15.2.1.3	Summary of Protocol Deviations – Safety Population
LISTINGS	
15.3.1.1	Listing of Inclusion/Exclusion Criteria
15.3.1.10	Listing of Subject Disposition, Randomization and Assignment to Analysis Sets
15.3.1.13	Listing of Protocol Deviations
15.3.2.7	Listing of Subject and Observations Excluded from Efficacy Analysis
16.1.7	Listing of Randomization Schemes and Codes

12.3 Demographics and Other Baseline Characteristics

Demographic and baseline characteristics will be summarized for the Safety Population and FAS, and listed for all screened subjects.

The demographic variables age, sex, race, body weight, height and BMI will be summarized by actual exposure, and by the two stratification factors (sex, and CC consumption). Other baseline characteristics will also be included in the table.

No inferential analyses will be presented for the demographic and baseline characteristics.

The data will be presented in the below outputs, the TFL number refers to the TFL number in the accompanying TFL shell document:

TFL number	Title
TABLES	
15.2.1.4.1	Summary of Demographics and Other Baseline Characteristics – Safety Population
15.2.1.4.2	Summary of Demographics and Other Baseline Characteristics – FAS

TFL number	Title
15.2.1.4.2.1	Summary of Demographics and Other Baseline Characteristics by Sex – FAS
15.2.1.4.2.2	Summary of Demographics and Other Baseline Characteristics by Cigarette Consumption – FAS
LISTINGS	
15.3.1.9	Listing of Demographics

12.3.1 FTND Questionnaire at Screening

FTND score value and the number and percentage of subjects in each category (mild/moderate/severe) will be presented. Data will be listed and summarized as reported in Section 12.3 “Demographics and Other Baseline Characteristics”.

The data will be presented in the below outputs, the TFL number refers to the TFL number in the accompanying TFL shell document:

TFL number	Title
TABLES	
15.2.1.4.1	Summary of Demographics and Other Baseline Characteristics – Safety Population
15.2.1.4.2	Summary of Demographics and Other Baseline Characteristics – FAS
15.2.1.4.2.1	Summary of Demographics and Other Baseline Characteristics by Sex – FAS
15.2.1.4.2.2	Summary of Demographics and Other Baseline Characteristics by Cigarette Consumption – FAS
LISTINGS	
15.3.1.12	Listing of Fagerström Test for Nicotine Dependence Results

12.3.2 Current Cigarette Brand and Smoking Characteristics

The following smoking characteristics at Admission (Day -2) will be summarized and listed as specified in Section 12.3 “Demographics and Other Baseline Characteristics”. ISO tar yields (continuous and categorized as 1-5 mg, 6-8 mg, 9-10 mg and > 10 mg), and number of CCs smoked on a daily basis during the previous 4 weeks (continuous and categorized as 10-19 CC/day and >19 CC/day).

Current CC brand(s) smoked by the subject and recorded at the Screening Visit and Admission (Day -2) will be summarized and listed by actual exposure and study day for the Safety Population. This will include brand name(s) and ISO nicotine, tar, and CO yields. Data at screening will be listed only.

Smoking history, including whether subjects have smoked for at least the last three consecutive years and whether the subject smoked any mentholated CCs during the previous 4 weeks will be listed by actual exposure at Screening and Admission (Day -2) where applicable. Responses to planning to quit smoking during the next 3 months will be

listed at Screening. Readiness to accept interruption of smoking for up to 5 days and the advice on the risks of smoking and debriefing will be listed at Admission.

Data will be listed and summarized as presented in the below outputs, the TFL number refers to the TFL number in the accompanying TFL shell document:

TFL number	Title
TABLES	
15.2.1.4.1	Summary of Demographics and Other Baseline Characteristics – Safety Population
15.2.1.4.2	Summary of Demographics and Other Baseline Characteristics – FAS
15.2.1.4.2.1	Summary of Demographics and Other Baseline Characteristics by Sex – FAS
15.2.1.4.2.2	Summary of Demographics and Other Baseline Characteristics by Cigarette Consumption – FAS
15.2.1.5	Summary of Current Cigarette Brands – Safety Population
LISTINGS	
15.3.1.2	Listing of Current Cigarette Brands
15.3.1.3	Listing of Smoking History
15.3.1.5	Listing of Advice on Risks of Smoking
15.3.1.6	Listing of Willingness to Abstain from Smoking During the Next 3 Months
15.3.1.7	Listing of readiness to Accept Interruption of Smoking for up to 5 days

12.3.3 Medical History and Concomitant Diseases

Medical history is defined as any condition that started and ended prior to Screening. Medical history will be coded using MedDRA version 16.0 and listed separately by actual exposure, System Organ Class (SOC) and Preferred Term (PT) within SOC.

Medical History will be summarized by actual exposure, SOC and PT for the FAS.

Concomitant disease is defined as any condition diagnosed at Screening or was ongoing at Screening. Concomitant disease will be coded using MedDRA version 16.0 and listed separately by actual exposure, SOC and PT within SOC.

Concomitant disease will be summarized by actual exposure, SOC and PT for the Safety Population.

Partial dates will not be imputed, but assumptions will be made as follows to assign to either medical history or concomitant diseases:

Date information	Assign as
Missing stop date	Concomitant disease
Partial date, e.g. --May2012, or -----2011. If month/year is the same as, or later than the month and/or year of Screening.	Concomitant disease
Partial date, e.g. --May2012, or -----2011. If month and/or year is earlier than the month and/or year of Screening.	Medical history

The data will be presented in the below outputs, the TFL number refers to the TFL number in the accompanying TFL shell document:

TFL number	Title
TABLES	
15.2.1.6	Summary of Medical History – Safety Population
15.2.1.7	Summary of Concomitant Diseases – Safety Population
LISTINGS	
15.3.1.11	Listing of Medical History and Concomitant Diseases

12.3.4 Other Data

Other data collected at Screening and/or Admission will be listed by actual exposure. These data are as follows:

- Cotinine urine test
- Urine pregnancy test
- Chest x-ray
- Urine drug screen
- Serology (excluding HIV status).
- Alcohol breath test
- Prior medication
- Debriefing and risk of smoking
- Willingness to use THS 2.2

Willingness and ability to use the products will also be summarized.

The data will be presented in the below outputs, the TFL number refers to the TFL number in the accompanying TFL shell document:

TFL number	Title
TABLES	
15.2.6.10.1	Summary of Prior Medication by Anatomical Therapeutic Classes (ATC) 1 and 2 – Safety Population
15.2.6.10.2	Summary of Prior Medication by Preferred Term – Safety Population
LISTINGS	
15.3.1.4	Listing of Product Test and Willingness to Use the Product
15.3.1.8	Listing of Safety Laboratory Entry Criteria
15.3.6.3	Listing of Prior and Concomitant Medication

12.4 Measurements of Product Compliance

During the confinement period, compliance to product/regimen allocation (exclusive use of THS 2.2 and CC in THS 2.2 and CC arms, respectively, and full abstinence from smoking in the SA arm) will be ensured by strict distribution of each THS Tobacco Stick/CC when requested by the subject.

In addition, levels of CO in exhaled breath will be measured in the SA arm to ensure that the subjects have not smoked any cigarettes. This will serve as a compliance tool during the confinement period. These data (continuous and categorical) will be summarized and listed by actual exposure.

The data will be presented in the below outputs, the TFL number refers to the TFL number in the accompanying TFL shell document:

TFL number	Title
TABLES	
15.2.5.1	Summary of Compliance as Measured by Exhaled CO (ppm) in the SA Arm- Safety Population
LISTINGS	
15.3.3.2	Listing of Secondary Biomarkers and Sampling/Collection Times

12.5 Extent of Exposure (Product Consumption)

Details of the product test prior to enrollment and of daily product use after randomization will be listed and summarized.

The data will be presented in the below outputs, the TFL number refers to the TFL number in the accompanying TFL shell document:

TFL number	Title
TABLES	
15.2.2.1	Summary of Use of THS 2.2 Product and CC – Safety Population
LISTINGS	
15.3.2.1	Listing of Product Usage
15.3.2.2	Listing of Cigarette Butt and THS Tobacco Stick Collection Data

12.6 Planned Statistical Analyses

Markedly non-lognormally distributed BoExp data will be transformed or analyzed by appropriate non-parametric methods with bootstrapping using the SAS procedure PROC SURVEYSELECT. The seed to be used in any analysis will be contained in the SAS output and will be different for each analysis.

For all statistical analysis data from all arms, THS 2.2, CC and SA will be included in all models.

12.6.1 Primary Analyses

12.6.1.1 Primary Biomarkers of Exposure in 24 hour collection

The primary BoExp (COHb in blood and urinary concentrations adjusted for creatinine of MHBMA, 3-HPMA and S-PMA) will be summarized as detailed in Section 12.1.3 “Descriptive Statistics”.

The baseline is as defined in Section 12.1.4 “Definitions for Statistical Data Analysis”,

The values and percent changes in the concentration adjusted for creatinine will be listed and summarized along with the COHb concentrations and percent changes from baseline. In addition line graphs will be produced for means (and 95% CI) over all timepoints.

For all arms the 24 hour urine collection will be collected daily from Day -1 to Day 5. Although the 24 hour urine collection will span into the following Day it will be reported by the day the collection started.

The primary endpoints will be log-transformed (base_e) prior to analysis. The analysis will compare (1) last Day 5 values of COHb in blood and (2) urinary concentrations of MHBMA, 3-HPMA and S-PMA corrected for creatinine on Day 5 between the THS 2.2 and CC arms. An ANCOVA (Snedecor and Cochran 1982) model will be used with terms for the log-transformed baseline value, sex, average daily CC consumption over the last 4 weeks as reported during screening and product.

The SAS code to be used is shown below:

```
Proc mixed data=_data_ ;
Class product sex cigarette_cons ;
Model log (Day 5) = log (baseline) sex cigarette_cons product ;
Lsmean product / pdiff =control('CC') alpha=0.05 cl ;
Run ;
```

The least squares (LS) means and estimate of the difference along with it's 95% CI will be back-transformed before presenting in the tables. The geometric LS means for each product along with the ratio (THS 2.2 : CC) and 95% CI will be presented in the tables.

In addition line graphs will be produced for product means (and 95% CI) over all timepoints for COHb in blood and urinary concentrations adjusted for creatinine of MHBMA, 3-HPMA and S-PMA.

The data will be presented in the below outputs, the TFL number refers to the TFL number in the accompanying TFL shell document:

TFL number	Title
FIGURES	
15.1.1.1	Blood COHb (%) Mean and 95% CI– FAS
15.1.1.2	MHBMA Urinary Concentration Adjusted for Creatinine (units) Mean and 95% CI – FAS
15.1.1.3	3-HPMA Urinary Concentration Adjusted for Creatinine (units) Mean and 95% CI– FAS
15.1.1.4	S-PMA Urinary Concentration Adjusted for Creatinine (units) Mean and 95% CI– FAS
15.1.1.5	Blood COHb (%) % Change from Baseline Mean and 95% CI– FAS
15.1.1.6	MHBMA Urinary Concentration Adjusted for Creatinine (units) % Change from Baseline Mean and 95% CI – FAS
15.1.1.7	3-HPMA Urinary Concentration Adjusted for Creatinine (units) % Change from Baseline Mean and 95% CI– FAS
15.1.1.8	S-PMA Urinary Concentration Adjusted for Creatinine (units) % Change from Baseline Mean and 95% CI– FAS
TABLES	
15.2.3.1	Analysis of Blood COHb (%) versus CC on Day 5 – FAS
15.2.3.2	Analysis of MHBMA Urinary Concentration Adjusted for Creatinine (units) versus CC on Day 5 – FAS
15.2.3.3	Analysis of 3-HPMA Urinary Concentration Adjusted for Creatinine (units) versus CC on Day 5 – FAS
15.2.3.4	Analysis of S-PMA Urinary Concentration Adjusted for Creatinine (units) versus CC on Day 5 – FAS
15.2.3.5	Descriptive Statistics of % Change in Primary Biomarkers of Exposure on Day 5 – FAS
15.2.3.5.1	Descriptive Statistics of % Change in Primary Biomarkers of Exposure on Day 5 by Sex – FAS

TFL number	Title
15.2.3.5.2	Descriptive Statistics of % Change in Primary Biomarkers of Exposure on Day 5 by Cigarette Consumption – FAS
15.2.3.6	Descriptive Statistics of Blood COHb (%) – FAS
15.2.3.6.1	Descriptive Statistics of Blood COHb (%) by Sex – FAS
15.2.3.6.2	Descriptive Statistics of Blood COHb (%) by Cigarette Consumption – FAS
15.2.3.7	Descriptive Statistics of MHBMA Urinary Concentration Adjusted for Creatinine (units) – FAS
15.2.3.7.1	Descriptive Statistics of MHBMA Urinary Concentration Adjusted for Creatinine (units) by Sex – FAS
15.2.3.7.2	Descriptive Statistics of MHBMA Urinary Concentration Adjusted for Creatinine (units) by Cigarette Consumption – FAS
15.2.3.8	Descriptive Statistics of 3-HPMA Urinary Concentration Adjusted for Creatinine (units) – FAS
15.2.3.8.1	Descriptive Statistics of 3-HPMA Urinary Concentration Adjusted for Creatinine (units) by Sex – FAS
15.2.3.8.2	Descriptive Statistics of 3-HPMA Urinary Concentration Adjusted for Creatinine (units) by Cigarette Consumption – FAS
15.2.3.9	Descriptive Statistics of S-PMA Urinary Concentration Adjusted for Creatinine (units) – FAS
15.2.3.9.1	Descriptive Statistics of S-PMA Urinary Concentration Adjusted for Creatinine (units) by Sex – FAS
15.2.3.9.2	Descriptive Statistics of S-PMA Urinary Concentration Adjusted for Creatinine (units) by Cigarette Consumption – FAS
LISTINGS	
15.3.3.1	Listing of Primary Biomarkers

The listing of the urinary biomarkers will include the concentration, the percent change in the concentration, the concentration adjusted for creatinine, the percent change in the concentration adjusted for creatinine, the volume of urine in the 24 hour collection, the quantity excreted over 24 hours and the percent change in quantity excreted over 24 hours.

The listing of the COHb data will include the concentration, the percent change in the concentration, and a flag for whether a subject's COHb is <2%.

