7.5.1 Biomarker of Exposure

7.5.1.1 Exhaled CO and Carboxyhemoglobin

Carboxyhemoglobin measured in blood and exhaled CO will be investigated as a measure of CO in all three study arms. The CO breath test should be conducted in timely conjunction with the blood sampling for COHb, where applicable. In the SA arm, the CO breath test will serve as a verification of compliance (Section 6.5.4).

CO Breath Test

Carbon monoxide in exhaled breath will be measured using the Smokerlyzer[®] such as Micro 4 Smokerlyzer[®] device or similar.

On Days -1 to Day 5, the CO breath test will be conducted four times per day. The first test should be conducted within 15 minutes prior to the first product use. The other three tests should be conducted as described in section 9.

Confidentiality statement: Data and information contained in this document are considered to constitute trade secrets and confidential commercial information, and the legal protections provided to such trade secrets and confidential information are hereby claimed under the provisions of applicable law. No part of this document may be publicly disclosed without the written consent of Philip Morris Products S.A.

For subjects in the SA arm, the first CO breath test will be done between 08:00 AM-09:30 AM. The other three tests should be conducted as described in section 9.

On Day -2, Day 6, the CO breath tests will be conducted once irrespective of time of product use.

Carboxyhemoglobin

Assessment for COHb measurement will be performed at the local laboratory. Carboxyhemoglobin in blood will be assessed on a daily basis, starting from Day -1 until Day 5.

On Day -1 to Day 4: one blood sample will be collected between 08:00 PM-09:30 PM.

On Day 5: one blood sample will be collected within 15 minutes prior to the first product use. The three other blood samples will be collected as described in section 9.

For subjects in the SA arm, the first COHb will be done between 08:00 AM-09:30 AM. The three other blood samples will be collected as described in section 9.

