12.6.2 Secondary Analyses

12.6.2.1 Biomarkers of Exposure

In addition, the quantity excreted over 24 hours for MHBMA, 3-HPMA and S-PMA will be presented.

The PP Population will be used to examine the robustness of the analysis of the primary endpoints. The primary analysis on the FAS will be repeated on the PP population using the same methodology as detailed in Section 12.6.1.1 “Primary Biomarkers of Exposure in 24 hour collection”.

The primary BoExp will also be examined to compare the reductions in THS 2.2 vs. SA using the same methodology as for the primary analysis.

The secondary BoExp are exhaled CO, total 1-OHP in urine, Total NNN in urine, 4-ABP in urine, 1-NA in urine, 2-NA in urine, o-tol in urine, CEMA in urine, HEMA in urine, B[a]P in urine, HMPMA in urine, S-BMA in urine, Total NNAL in urine and NEQ in urine. The urine parameters will be expressed as concentrations adjusted for creatinine and the quantity excreted over 24 hours.

The baseline of the exhaled CO will be the time-matched measurements on Day 0, i.e. the 1st measurement on Days 1 to 5 will be matched to the 1st measurement on Day 0 and similarly for the 2nd, 3rd and 4th measurements. The baseline of the urinary biomarkers will be the last assessment prior to 06:29 AM on Day 1.

The values and percent changes for urinary BoExp in the quantity excreted over 24-hours and the concentration adjusted for creatinine will be listed and summarized. In addition line graphs will be produced for product means (and 95% CI) over all timepoints.

CO in exhaled breath will be measured using the Micro+™ Smokerlyzer® or similar device, conducted on Day -2 to Day 6. On Day -1 to Day 5 the first test per day will be performed within 15 minutes prior to the first product use and then between 12:00 and 01:30 PM, between 04:00 and 05:30 PM and between 08:00 and 09:30 PM. On Days -2 and Day 6 the CO breath tests will be conducted once.

Descriptive statistics summarized by exposure will be produced separately for all timepoints for all visits applicable for exhaled CO. This will be done on the FAS, stratified by sex, and CC consumption.

Actual values and percent changes from baseline in levels of exhaled CO will be listed and summarized. In addition line graphs will be produced for product means (and 95% CI) over all timepoints.

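### COHb percent change is tied to one evening baseline, so three of the four Day 5 draws can show a fall that is only time of day; the primary comparison is unaffected when the evening sample is present

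*SAP*

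**What the plan says.** **Baseline.** For the primary biomarkers, SAP 12.6.1.1 states: "The baseline is as defined in Section 12.1.4". That section (SAP 12.1.4) gives: "The last assessment prior to 06:29 AM on Day 1". No COHb-specific baseline overrides it.

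**Sampling.** Protocol 7.5.1.1 sets the schedule: "On Day -1 to Day 4: one blood sample will be collected between 08:00 PM-09:30 PM". The last COHb value before the cut-off is therefore the Day 0 evening sample. On Day 5 there are four draws. For the THS 2.2 and CC arms the first is before use: "On Day 5: one blood sample will be collected within 15 minutes prior to the first product use". In the SA arm it is taken at 08:00-09:30 AM. SAP 11.3 (Table 16) places the other three at 12:00-01:30 PM, 04:00-05:30 PM and 08:00-09:30 PM.

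**Percent change.** SAP 7 defines it as the value at the time point minus the subject's baseline, divided by that baseline. SAP 12.6.1.1 applies it to COHb, since the urinary results are to be "summarized along with the COHb concentrations and percent changes from baseline". It also plans line graphs over all time points, and lists Figure 15.1.1.5: "Blood COHb (%) % Change from Baseline Mean and 95% CI". The COHb listing also carries percent change. Table 15.2.3.5 reports Day 5 percent change without saying which of the four COHb samples it uses.

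**Primary comparison.** "The analysis will compare (1) last Day 5 values of COHb in blood", with log baseline as covariate.

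**Related measures.** For the other CO measure, SAP 12.6.2.1 says: "The baseline of the exhaled CO will be the time-matched measurements on Day 0". For plasma nicotine and cotinine, SAP 12.6.2.2 restricts the change from Day 0 to the Day 5 sample nearest 08:00 PM.

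**The concern.** COHb falls overnight when smoking is not allowed and rises again through the day. Dividing a pre-use, noon or afternoon value by an evening baseline mixes that daily cycle with any effect of the assigned product. Followed as written, the percent-change rule lets the CC arm show a reduction on Day 5 although nothing in its exposure has changed, and it adds the same component to the falls in the THS 2.2 arm.

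At stake is how the within-arm descriptions of a primary biomarker are read. The SAP handles the same problem for exhaled CO by time-matching, and for nicotine and cotinine by limiting the change to the evening sample. COHb has no equivalent rule.

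**Working it through.** The documents state no size for the daily COHb swing, so there is no planned figure to reproduce. The check asks what percent change a CC smoker would show if smoking did not change at all.

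**Inputs from the documents**
- Smoking window 06:30 AM to 11:00 PM (Protocol 4.1, SAP 6.1): 16.5 h on, 7.5 h off.
- Day 5 sampling windows as above; midpoints 12:45 PM, 04:45 PM and 08:45 PM. The pre-use draw is put at 06:30 AM.
- Half-life: Protocol 4.2 says only that the primary biomarkers average 24 h or less. A COHb half-life T is therefore an assumption, varied from 2 to 24 h.

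**Overnight decay alone.** From 11:00 PM to the earliest possible draw at 06:15 AM is 7.25 h. The fraction remaining is 2^(-7.25/T): 0.187 at T = 3 h and 0.433 at T = 6 h, which are falls of 81% and 57%. On this formula the fall exceeds 50% only if T is below 7.25 h.

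**Full daily cycle.** Assume uniform intake during the smoking window, first-order elimination and a repeating 24-h cycle. With the level expressed as a fraction of its plateau and t in clock hours:
- level at 06:30 AM: c0 = (1 - 2^(-16.5/T)) × 2^(-7.5/T) / (1 - 2^(-24/T))
- level during smoking hours: C(t) = 1 - (1 - c0) × 2^(-(t - 6.5)/T)
- spurious change = C(t) / C(20.75) - 1

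Example, T = 4 h: c0 = 0.9427 × 0.2726 / 0.9844 = 0.261. C at 12:45 PM = 0.750, at 04:45 PM = 0.875, at 08:45 PM = 0.937. The changes are 0.261/0.937 - 1 = -72%, 0.750/0.937 - 1 = -20% and 0.875/0.937 - 1 = -7%.

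| Assumed half-life | Pre-use 06:30 AM | 12:45 PM | 04:45 PM |
|---|---|---|---|
| 2 h | -93% | -10% | -2% |
| 3 h | -82% | -17% | -5% |
| 4 h | -72% | -20% | -7% |
| 5 h | -64% | -21% | -8% |
| 6 h | -57% | -21% | -8% |
| 8 h | -46% | -19% | -8% |
| 12 h | -33% | -15% | -7% |
| 24 h | -18% | -9% | -4% |

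**Sensitivity**
- At the edges of the sampling windows, noon runs from -7% to -25% and afternoon from -1% to -11% over all half-lives tried.
- A non-smoking background equal to 10% of the evening level shrinks each figure by a tenth.
- If Table 15.2.3.5 averaged all four draws, the spurious change would be -8% to -26%.

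**After the fix.** Day 5 evening against Day 0 evening gives 0 at matched times, and at most about 2.4% when the two draws sit at opposite ends of the 08:00-09:30 PM window.

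**The case against.** The strongest reply is that a reader might infer more than the text supports.

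- **Bias in the success criterion.** The documents do not support this. Success (SAP 5.5.2) is a 50% reduction in THS 2.2 relative to CC, estimated as a between-arm ratio. With complete sampling, both the endpoint and its covariate are evening values. No section judges a within-arm percent change against 50%. THS 2.2 and CC also remain comparable at the same nominal draw, because their schedules are the same. This stands in full.
- **A large artefact at all three non-evening draws.** Only the pre-use value is strongly affected, and its size depends on an assumed half-life. This stands.
- **An earlier draw replacing a missing evening sample in the primary test.** That is one reading of the last Day 5 value. The last scheduled sample is another, and SAP 12.1.5 says missing data will in general not be imputed. No rate of missing evening samples is given. What remains is a wording gap.
- **Coverage of the percent change.** The SAP does not say outright that it covers each Day 5 draw. Table 15.2.3.5 could be evening only, and layout is left to a separate shell document. Figure 15.1.1.5 is not among the topline outputs in SAP 13.3, although Table 15.2.3.5 is. This makes the effect on that table a possibility. It does not remove the problem, because the general rule in SAP 7 contains no exception.
- **Time-matching is impossible for COHb.** True, since no morning or midday baseline was drawn. That argues for leaving those percent changes out, as the nicotine rule does; computing them against an evening value is not a substitute.

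**Conclusion.** The point holds as a defect in descriptive outputs. Read as written, SAP 7, 12.1.4 and 12.6.1.1 refer every COHb percent change to one evening sample, so the percent changes at three of the four Day 5 draws are confounded with time of day. At the pre-use draw the effect is large under an assumed half-life of 3 to 6 h and modest at 24 h; at noon it is moderate and in the afternoon small. All sizes rest on the uniform-intake, first-order model and on half-lives that the documents do not supply. The direction rests only on the overnight smoking pause.

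The plan does not show a bias in the primary ANCOVA when the evening sample is present. One conflict does need settling: SAP section 9 describes a COHb model with a product-by-time-point interaction whose main comparison runs over all time points, whereas SAP 12.6.1.1 uses the last Day 5 value. Under the section 9 reading, non-evening values would enter the model alongside an evening baseline. Severity is minor to moderate.

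**What to change.** In SAP 12.6.1.1:

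1. Calculate COHb percent change only for the 08:00-09:30 PM samples, Days 1 to 5 against Day 0 evening. This follows what SAP 12.6.2.2 already does for Day 5 nicotine and cotinine. State it in the specifications for Figure 15.1.1.5, Table 15.2.3.5 and the COHb listing.
2. Show the pre-use, noon and afternoon Day 5 draws as values or between-arm ratios, noting that the SA arm's first draw is at 08:00-09:30 AM and not before first use.
3. Name the 08:00-09:30 PM sample as the primary Day 5 COHb value, missing if it was not drawn.
4. Reconcile this with SAP section 9, so that a single comparison is identified as the main one for COHb.

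The cost is SAP and table-shell wording. No new data are needed.
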